4.11 DEFINITIONS RELATED TO ESTIMANDS

Sections 7 and 8 specify analytical approaches for the primary and secondary endpoints using the estimand framework. An estimand is a precise description of the quantity that is estimated to assess the treatment effect reflecting the clinical question posed by a given clinical trial objective. It has five attributes: population,

treatment, variable of interest, e.g., outcome and timepoint, summary measure, and possible intercurrent events (defined as an event that can occur post-randomisation and preclude or affect the interpretation of the variable of interest, e.g. discontinuation of treatment). Intercurrent events specific to this trial are described in Section 6.5, 'Intercurrent events'.

When defining an estimand, it must be clear how intercurrent events will be handled in the analysis. Different approaches can be taken towards handling intercurrent events and are described below:

- i) *Hypothetical*: a strategy that envisages a scenario in which the intercurrent event would not occur, e.g., if participants had not switched treatment or if death had not occurred
- ii) *Treatment policy*: a strategy that seeks to understand the treatment effect on the variable regardless of the intercurrent event, i.e., an outcome is of interest whether or not the intercurrent event occurred before the outcome, e.g. the outcome is of interest irrespective of whether the participant takes additional medication.
- iii) *Composite*: a strategy that considers the occurrence of the intercurrent event as informative about the participants' outcome. Under this strategy, the intercurrent event is included in the endpoint definition, e.g., classifying the use of rescue medication as failure, in addition to disease progression, in a time-to-event analysis.
- iv) *Principal Stratification*: a strategy wherein treatment effects are assessed in the stratum of participants who would have a specific status with respect to the intercurrent event, e.g., examining the effect of treatment in participants who would not require rescue medication
- v) *While-on-treatment*: a strategy that considers response to treatment before the occurrence of the intercurrent event to be of interest. For repeated measures, values up to the intercurrent event are of interest but not values after the intercurrent event. Generally, this strategy is only useful if the duration of treatment is not relevant either because it is not clinically relevant or because the rate of an event or outcome is constant over time, e.g. the rate of adverse events, where one assumes a constant hazard.

4.12 ESTIMAND-TO-ANALYSIS TABLES

To incorporate the estimand framework into the SAP, we use "estimand-to-analysis" tables, as described by Kang, *et al.* 2022:

"The estimand-to-analysis table template starts with the study objective describing the clinical question of interest as written in the trial protocol. The remainder of the table describes each attribute of the estimand (treatment, target population, variable, intercurrent events, and population-level summary) in the left column (ESTIMAND), while the right column describes how each attribute will be handled using the data collected in the clinical trial (ANALYSIS)."⁵

5 DESCRIPTIVE STATISTICS

5.1 PARTICIPANT DISPOSITION

A CONSORT flow diagram will be used to summarise the study population from screening to analysis, including the number of people who were:

- Screened for eligibility
 - and were eligible at screening
 - and were ineligible at screening (screen failures)*
- Eligible at screening but not randomised*
- Ineligible at screening but randomised (protocol violation)*
- Eligible and randomised (or not randomised for the control group)

[Subsequent numbers will be given by study group]

- Allocated to each study group
 - and received the allocated vaccine
 - and did not receive the allocated vaccine*
- Included in the Reactogenicity and Safety Population (according to vaccine received not allocated)[^]
- Included in the Primary Day-28 Immunology Population[^]
- Included in the Month-6 Immunology Population[^]
- Included in the Month-12 Immunology Population[^]

* Reasons will be provided.

[^]The number of participants with missing data will be noted. Missing data arising from lost-to-follow-up or withdrawal will be enumerated, including the level of withdrawal (from intervention, follow-up, or both, and consent to use data up to the time of withdrawal) and reasons (harms-related reasons for withdrawal will be emphasised).

5.2 PATIENT CHARACTERISTICS AND BASELINE COMPARISONS

Baseline and demographic characteristics, including stratifying variable (age group) will be described by study group; see Dummy Table 1. Categorical variables will be described with the number in each category and corresponding percentage of the whole study group. Normally distributed continuous variables will be described by the mean, standard deviation, and minimum and maximum values. Non-normally distributed continuous variables will be described by the median, 25th and 75th percentiles, and minimum and maximum values. Statistical tests for differences between study groups at baseline will not be performed.

5.3 ADHERENCE AND PROTOCOL DEVIATIONS

Adherence to the intervention is defined as receiving a trial booster vaccination on Day 0. The number and percent of participants who adhered will be presented by study group.

Pre-defined major protocol deviations (with a direct bearing on the primary outcome) are:

- Inclusion and randomisation of an ineligible person
- Receiving the wrong trial vaccination
- Day-28 visit occurring outside of the specified time window (between Day 25 and 35 [inclusive], with Day 0 being the day of trial vaccination)

All protocol deviations will be classified as minor or major before unblinding. Major protocol deviations are those that are deemed to significantly affect the rights or safety of a trial participant, or the reliability, accuracy, and robustness of the data. The number and percentage of patients with major and minor protocol deviations will be summarised by study group (as per randomisation), with details of type of deviation provided.

5.4 CONCOMITANT MEDICATIONS

Concomitant medications at baseline and throughout the study period will be described by study group. New medications taken during the trial in response to a local or general reaction or an AE will also be recorded. For AEs, the medication taken will be included in a line list of all AEs.

6 OUTCOME VARIABLES AND OTHER PARAMETERS

6.1 OUTCOME VARIABLES AS DEFINED IN THE PROTOCOL

6.1.1 Primary outcomes

The primary outcomes (as defined in the protocol) are:

Immune response

Binding antibodies – These will be evaluated using the commercial Euroimmun S1 IgG ELISA (Wuhan and Omicron [once available]) on serum collected at four timepoints (baseline, 28 days, 6 months, and 12 months) for the two vaccine groups and three timepoints (baseline, 6 months, and 12 months) for the control group.

Reactogenicity

Reactogenicity for vaccine groups (A&B) will be measured using the accepted standardised method to evaluate systemic and local side effects following vaccination using a structured questionnaire for seven days post-vaccination, as outlined in Table 1 in the protocol.

6.1.2 Secondary outcomes

The secondary outcomes (as defined in the protocol) are:

Immunogenicity

- Functional antibody – All samples will be assayed using the GenScript cPass SARS-CoV-2 Neutralization Antibody detection kit for WT and Omicron variant RBD antigen or other key newly emerging variants. Samples will be tested on serum collected at four timepoints (baseline, 28 days, 6 months, and 12 months) for the two vaccine groups and three timepoints for the control group.
- Neutralising antibody - A fraction of samples (20%) will be assessed using a SARS-CoV-2 assay at the PDI, Melbourne. Testing will be at the same time points as for binding antibodies for Wuhan strain and two Variants of Concern (VoC), including Omicron or other key newly emerging variants.
- Cellular immunity - Cellular immunity will be assessed on 50% of participants per group of samples collected at four timepoints for the two vaccine groups and three timepoints for the control group as follows:
 - QuantiFERON Human IFN- γ SARS-CoV-2 (Qiagen) will be performed using heparinised whole blood (Wuhan).
 - Peripheral blood mononuclear cells (PBMCs) will be isolated by density gradient centrifugation within 12 hours of collection and stored in liquid nitrogen at MCRI. Assays will include IFN- γ Elispot, intracellular cytokine assays (flow cytometry) and multiplex cytokine assays (Wuhan and Omicron).

Safety

All solicited AEs will be collected for 7 days, all unsolicited AEs will be collected for 28 days, and all medically attended AEs will be collected for 3 months. SAEs will be collected throughout the 12-month follow-up period.

6.1.3 Exploratory outcomes

The exploratory outcomes (as described in the protocol) are:

- Previous infections (RAT or PCR positive or symptomatic with close contact) and vaccinations will be recorded at baseline.

- Breakthrough infections will be recorded and tested for during the study.
- Nasal swabs will be collected from all severe breakthrough cases and a subset of mild cases within three days of illness. A representative sample of positive samples will be processed for viral load and whole genome sequencing of SARS-CoV-2.
- We will explore differences in viral load, genome characteristics, and immunological markers among mild and severe breakthrough cases.

6.2 IMMUNOGENICITY OUTCOME VARIABLES

Table 3 lists the immunogenicity outcome variables including the units, and participant subsets in which the outcomes are measured. There may be additional immunogenicity outcome variables (e.g. for additional variants) that may become available after this SAP is written.

Table 3. Description of immunogenicity outcome variables, including units and subsets in which they are measured

	Outcome	Subset	Units
Main study	Binding antibody (IgG) (Euroimmun Wuhan)	All	BAU/ml
	Binding antibody (IgG) (Euroimmun Omicron BA.1)	All	RU/ml
	Binding antibody (IgG) (In-house assay Omicron BA.4/5)	All	EU/ml
	Binding antibody (IgG) (In-house assay Omicron JN.1)	All	EU/ml
	Binding antibody (IgG) (N-Protein)	All	EU/ml
	Functional antibody (C-PASS assay - sVNT Wuhan)	All	U/mL
	Functional antibody (C-PASS assay - sVNT Omicron BA.1)	All	U/mL
	Functional antibody (C-PASS assay - sVNT Omicron BA.4/5)	All	U/mL
	Neutralising antibody (Wuhan)	20% of samples	NT50
CMI sub-study	Neutralising antibody (variant of concern)*	20% of samples	NT50
	IFN γ	50% of participants	IU/ml

[^]Baseline measurements are also taken at Day 0

* Variants of concern to be confirmed

6.3 REACTOGENICITY AND SAFETY OUTCOMES

Table 4 summarises the reactogenicity and safety outcomes and relevant parameters. Further details on all collected parameters are stored in RedCAP Codebooks, as detailed in the Data Management Plan. Definitions of the terms adverse event, adverse reaction, and serious adverse event are given in the Protocol and are aligned with definitions used in trials involving investigational medicinal products.

Table 4. Reactogenicity and safety outcomes

Outcome	Parameter	Categories	Timepoints
Reactogenicity (local)	Pain		

Reactogenicity (general/systemic)	Tenderness	Grade 0, 1, 2, 3, or 4*	Day 1, 2, 3, 4, 5, 6, & 7
	Redness		
	Swelling		
	Hardness		
	Axillary lymphadenopathy		
	Warmth	Binary (presence/absence)	
	Itch		
	Fever		
Adverse Events to 28 Days	Nausea	Grade 0, 1, 2, 3, or 4*	Adverse Events to 28 Days: Day-0, -1, -7, and -28 visits, and Month-3 visit (for new information, e.g., resolution)
	Vomiting		
	Diarrhoea		
	Headache		
	Fatigue/Malaise		
	Myalgia		
	Arthralgia		
	Experienced an adverse event	Binary (yes/no)	
Adverse Reaction to 28 Days ^δ	System Organ Class [^]	As per MedDRA	Serious Adverse Events to 12 months: Unscheduled (participants instructed to contact study staff)
	Severity	Severity Grade 1 (mild), 2 (moderate), 3 (severe), 4 (life-threatening), 5 (fatal) [#]	
	Outcome	1-Resolved 2-Resolved with sequelae 3-Ongoing 4-Fatal 5-Unknown	
	Serious	Binary (yes/no)	
	Onset (days from trial vaccination)	Continuous	
	Event duration (days)	Continuous	
	Relatedness	1-Unrelated 2-Possible 3-Probable 4-Definite	

*5-point severity scale: 0-None; 1-Mild; 2-Moderate; 3-Severe; 4-Life-threatening. Refer to Protocol for more detailed definitions [#]Grade 3-4 events may be SAEs; all Grade 5 events are automatically considered SAEs. [^]Will require derivation from 'event_term' and 'saefin' fields by study team. ^δAn adverse reaction is an adverse event with causality assessment of either Possible, Probable, or Definite.

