	
Novavax (5µg of SARS-CoV-2 spike protein adjuvanted with 50µg of Matrix-M)

TRIAL DURATION	The recruitment period will be approximately 4-6 months. Each participant in the vaccine groups (A&B) will have ten visits, including their immunisation visit, with a follow-up period of 30 months. Group C will have eight visits.
PARTICIPANT DURATION	Participant duration will be 30 months. The vaccine groups (A & B) will have ten visits (three telephone calls and seven in-person). Group C will have eight visits (two telephone calls and six in-person). The DSMB will review participant safety data.

GLOSSARY OF ABBREVIATIONS

ABBREVIATION	TERM
AE	Adverse Event
ANOVA	Analysis of Variance
AR	Adverse Reaction
ATAGI	Australian Technical Advisory Group on Immunisation
BRF	Biobank Registration Form (MCRI)
CEPI	Coalition for Epidemic Preparedness Innovations
CMI	Cell mediated immunity
CRF / eCRF	Case Report Form / electronic Case Report Form
DSMB	Data Safety Monitoring Board
GCP	Good Clinical Practice
GLP	Good Laboratory Practices
GMP	Good Manufacturing Practices
GMC	Geometric mean concentration
HREC	Human Research Ethics Committee
IB	Investigator's Brochure
ICH	International Conference on Harmonisation
IM	Intramuscular
MCRI	Murdoch Children's Research Institute
PBMC	Peripheral blood mononuclear cells
PDI	Peter Doherty Research Institute
PI	Principal Investigator
QC	Quality Control
RGO	Research Governance Office
RCH	Royal Children's Hospital (Melbourne)
SAE	Serious Adverse Event
SAP	Statistical Analysis Plan
SAR	Serious Adverse Reaction
SoA	Schedule of Assessments

SOP	Standard Operating Procedure
SSI	Significant Safety Issue
SST	Serum separator tube
SUSAR	Suspected Unexpected Serious Adverse Reaction
TGA	Therapeutic Goods Administration
UAR	Unexpected Adverse Reaction
USM	Urgent Safety Measure
VoC	Variants of concern

INVESTIGATOR AGREEMENT

I have read the protocol entitled "A randomised controlled trial to assess the immunogenicity, safety and reactogenicity of a bivalent mRNA Moderna COVID-19 vaccine or a protein-based Novavax COVID-19 vaccine given as a fourth dose in healthy adults in Australia."

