4.4.1 Inclusion criteria

Each participant must meet all the following criteria to be enrolled in this trial:

1. Have received a third COVID-19 vaccine dose at least six months before the start of the study.

2. No confirmed SARS-CoV-2 infection by PCR or RAT within the last three months.
3. Willing and able to give written informed consent.
4. Aged 18 years or above.
5. Willing to complete the follow-up requirements of the study.

Note that subjects with comorbidities other than those listed below as contraindications will be included. Pregnant women or women who may become pregnant will be included.

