7.2.5 Visit 5 (3 Months) – all groups (A,B,C)

Study staff will contact the participant by phone and document any medically attended AE or SAE. Study staff will also document any new information regarding unsolicited adverse events with onset up to 28 days following vaccination, such as resolution. Information regarding unreported breakthrough infections since visit 4 will be collected.

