7.2.6 Visit 6 (6 Months) – all groups (A,B,C)

For all participants, 5mL of blood will be collected in an SST tube. For participants in the CMI subset, 5mL of blood for the Quantiferon test will be collected in a heparinised tube, and 20mL of blood for PBMC will be collected in a heparinised tube. Blood samples will be kept at room temperature and transferred to the laboratory within 3 hours of collection.

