7.2.8. Visit 8 (18 months) – all groups (A,B,C)

Prior to the 18 month visit, participants will be asked to attend the 18 month visit in-person for a blood draw. Further consent will be obtained prior to any additional blood sampling at 18 months.

All participants will have 5mL of blood collected in an SST tube. For participants in the CMI subset, 20mL of blood will be collected in a heparinised tube for PBMCs. Blood samples will be kept at room temperature and transferred to the laboratory within 3 hours of collection.

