7.2.8 Unscheduled visits

To document breakthrough infections, enrolled participants will be requested to contact the Study Team if they develop symptoms of COVID-19. They will all be asked to take a RAT test and, if they test positive, may be asked to take a second nasal swab. The second swab will be stored for sequencing. To enrol those with severe disease and those with higher viral load, the second swab will be requested for the first 5-10 cases per month who present within three days of symptom onset, plus any severe cases. A representative sample of positive nasal swabs will be chosen for whole genome sequencing following

the completion of the 12 month visit and at the end of the study. All positive RAT tests and details regarding symptoms will be documented for all participants.

An optional blood sample (10ml, i.e., 5ml sodium heparin + 5 ml SST tube) will be collected if the participant consents 28 days after a positive RAT test (convalescent blood). The convalescent blood sample will determine whether breakthrough infections boost SARS-CoV-2 specific immune responses in previously vaccinated or control group individuals by comparing them to immune responses from previous blood samples. CMI will also be accessed. We will explore the association between immune protection and viral variants and identify potential viral signatures associated with severe breakthrough infections and/or immune escape. The participant will otherwise continue with scheduled study visits. The study team will maintain telephone contact with all participants who test positive for the course of their illness and fully document all telephone calls. With the participant's permission, the study team will seek clinical data from the health care providers or hospital(s) if the subject becomes clinically ill.

In-between study visits, participants will be sent 3 monthly SMS messages to remind them to report all breakthrough infections.

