8.2 Capturing and eliciting adverse event/reaction information

Participants will be asked to record local and systemic AEs for 7 days (and longer if symptoms persist at day seven, until resolution or stabilisation) following vaccination in the electronic or paper diary card (solicited AEs). Unsolicited AEs - all local and systemic AEs occurring in the 28 days following vaccination observed by the Investigator or reported by the participant, whether attributed to study medication, will be recorded in the AE section of the eCRF.

Serious adverse events (SAEs) will be followed up for the duration of the trial. Adverse events of special interest will be categorised as per CEPI guidelines (17).

Any unexpected, serious, or unusual AE following immunisation will be reported to SAEFVIC (vaccine safety surveillance service) through SAFEVAC: Integrated Vaccine Safety website that automatically forwards reports to the TGA (<https://www.safevac.org.au/Home/Info/VIC>). Adults who experience a significant adverse event reported to SAEFVIC (<https://mvec.mcri.edu.au/saefvic/>) should be referred to the Victorian Specialist Immunisation Services (VicSIS) for review and management of future COVID-19 vaccination.

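### After the Month-3 call no visit description or reminder specifies an SAE enquiry, so for 9 of the 12 months in the defined SAE window capture is described only as participant-initiated

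*SAP*

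**What the plan says.** **How SAEs are found.** SAP 6.3, Table 4 lists scheduled contacts for adverse events to Day 28, with Month 3 for updates. For SAEs it gives "Serious Adverse Events to 12 months: Unscheduled (participants instructed to contact study staff"). This matches Protocol 7.2.1, where participants are told at Day 0 how to reach staff about an SAE or COVID-19 symptoms.

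**What the visits contain.** For the Month-3 call, Protocol 7.2.5 says "Study staff will contact the participant by phone and document any medically attended AE or SAE". The Month-6 description (7.2.6) opens with "For all participants, 5mL of blood will be collected in an SST tube" and stays with blood sampling. Month 18 is similar: "All participants will have 5mL of blood collected in an SST tube". Between visits, "participants will be sent 3 monthly SMS messages to remind them to report all breakthrough infections" (Protocol 7.2.8, Unscheduled visits).

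**How long SAEs are collected.** Protocol 3.2.2 and SAP 6.1.2 set a 12-month collection period. SAP Table 11, rows ix and x, label the SAE endpoints as running to study end but time them at the Month-12 visit. The Protocol 7.1 schedule runs SAE documentation across all ten visits, and Protocol 8.2 states "Serious adverse events (SAEs) will be followed up for the duration of the trial". The Protocol synopsis states "Participant duration will be 30 months".

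**Pregnancy.** Protocol 4.4.1 states "Pregnant women or women who may become pregnant will be included", and Protocol 8.1.1 counts a congenital anomaly or birth defect as an SAE.

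**The concern.** Safety of the fourth dose is a secondary objective, and SAEs are the only safety events meant to be collected beyond Month 3. Yet the plan prompts participants every three months about infections, an exploratory outcome, and describes no prompt for SAEs. Events left to participants to volunteer tend to be under-counted. A hospital admission that the participant thinks unrelated to a vaccine given months earlier is easily left unreported.

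The resulting counts would appear in SAP Table 11 (rows ix and x) and Dummy Table S 2 with no caveat about how they were obtained. The DSMB and the annual safety report would draw on the same data. Participants can learn their vaccine at Day 7, so willingness to volunteer an event could differ between arms. Pregnancy outcomes are a specific example: a pregnancy in its first half at Day 0 would, at term, end after Month 3, and no later contact is described as asking about it.

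**Working it through.** The plan states no figure on this point, so there is none to reproduce. The check reads the contacts in order, then does simple arithmetic on months.

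**Step 1: what each description specifies (Protocol 7.2, 5.2.7)**

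| Contact | Content described |
|---|---|
| Day 28 | Unsolicited AEs (A, B); any AEs by phone (C) |
| Month 3 call | Medically attended AEs and SAEs; infections |
| Month 6 | Blood |
| Month 12 | Blood, voucher, test results |
| Month 18 | Consent, blood |
| Month 24 | Consent, infections, blood |
| Month 30 | Infections, blood, voucher, test results |
| SMS every 3 months | Infections |
| Medication record after Day 28 | Vaccines, investigational products, immunosuppressants, COVID-19 treatments |

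The last described SAE enquiry is at Month 3. The later medication record would not reveal an admission unrelated to COVID-19. Telephone follow-up and provider or hospital data (Protocol 7.2.8, Unscheduled visits) are described for participants who test positive.

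**Step 2: the SAE window**

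| Source | Window |
|---|---|
| Protocol 3.2.2; SAP 6.1.2; SAP Table 4 | 12 months |
| SAP Table 11 ix, x | Named study end, timed at Month 12 |
| SAP Table 2 | Visits 1 to 7, ending at Month 12 |
| Protocol 7.1 | Visits 1 to 10, ending at Month 30 |
| Protocol 8.2 | Followed up for the trial's duration |

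**Step 3: unprompted share**

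- 12-month window: 12 − 3 = 9 months; 9/12 = 75%.
- 30-month reading: 30 − 3 = 27 months; 27/30 = 90%.

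**Step 4: illustration.** The SAE rate (2 to 4 per 100 person-years) and the share volunteered (50 to 80%) are assumptions; neither document gives them.

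- Person-time, 450 vaccinees, no dropout: 450 × 9/12 = 337.5 person-years.
- SAEs occurring: 337.5 × 0.02 = 6.75 to 337.5 × 0.04 = 13.5, about 7 to 14.
- SAEs missed: 6.75 × (1 − 0.80) = 1.35 to 13.5 × (1 − 0.50) = 6.75, about 1 to 7.
- If the roughly 20% loss allowed for in Protocol 11.1 had all occurred by Month 3: 337.5 × 0.80 = 270 person-years, giving 5.4 to 10.8 SAEs. Missed: 5.4 × 0.20 = 1.08 to 10.8 × 0.50 = 5.4, about 1 to 5.

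**The case against.** The strongest reply is that silence in the visit paragraphs proves little. They are not exhaustive: Visits 6 to 8 also omit any infection question, and none of Visits 6 to 10 mentions recording medication, although Protocol 7.1 and 5.2.7 require both. Protocol 7.1 carries the SAE row across every visit, and staff see participants in person from Month 6 on. Call scripts and eCRFs are not among the documents, and details are deferred to the REDCap codebooks and the Data Management Plan. Table 4 is itself incomplete, because it labels all 12 months as unscheduled although the Month-3 call asks about SAEs.

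Much of this stands. A reader might infer that nobody asks about SAEs after Month 3; the documents do not establish that. But the case does not rest on silence alone. Table 4 names a passive method, and no visit description or reminder after Month 3 contradicts it. If the eCRF does contain the question, Table 4 is wrong and still needs correcting.

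Three other strong readings also fail:

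- **That 27 of 30 months is the size of the gap.** It holds only under Protocol 7.1 and 8.2. The defined outcome, including Table 4 itself, stops at 12 months, and following up an SAE need not mean collecting new ones.
- **That the pregnancy gap defeats the SAE definition.** It does not: participants are told how to report any SAE. An outcome question is a useful addition, not the repair of a contradiction.
- **That the arm comparison is biased.** Knowledge of allocation after Day 7 makes differential reporting possible, but nothing shows it will occur. Asking would reduce the risk without removing it.

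**Conclusion.** The point holds in limited form. After Month 3 the plan specifies no SAE enquiry, and the SAP describes capture as unscheduled and participant-initiated. That covers 75% of the 12-month window, or 90% of follow-up if the window is the whole trial; the documents must settle which applies. The SAE frequencies would tend to be too low, by about 1 to 7 events among 450 vaccinees over 9 months if the assumed rates are near the truth. The direction is better supported than the size.

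The consequence is confined to descriptive safety tables and the safety data under review. The primary endpoint and the sample size are unaffected. The change is worth making because the remedy uses contacts that already exist, but it is not critical to the trial's main conclusion.

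**What to change.** 1. Add one standard item to the procedures and eCRF for Visits 6 and 7: since the last contact, any hospital admission, life-threatening event, new disability or other SAE, and the outcome of any pregnancy, including one present at baseline. Add SAEs to the existing three-monthly SMS.
2. State one SAE collection window in Protocol 3.2.2, 7.1 and 8.2 and in SAP 6.1.2, Table 4 and Table 11. If it runs past 12 months, use the same item at Visits 8 to 10, subject to consent and ethics approval for those visits. The further consent in Protocol 4.9 is described for infection information and blood samples, so its wording may need to change.
3. Amend SAP Table 4 to list the visits at which SAEs are asked about, plus unscheduled reports. State in the report that SAEs from any period without a prompted enquiry were passively reported. Where Visits 6 and 7 have already passed, the item at the next contact can recover part of the history, within the limits of recall.

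**Cost.** A minor protocol and SAP amendment, one eCRF item and a changed SMS text, with no new visit or sample. There will be more SAE forms to process and a less favourable SAE count. The Month-30 visit depends on funding, so that contact cannot be relied on.
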